### C. Study Design

We propose to use a randomized control trial design and recruit 230 18-28 year old men and women over a 42-month period to address the proposed aims. Participants will be randomly assigned to an experimental condition (sugar-sweetened beverage [SSB] or unsweetened, flavored control [USB]) and then to one of two flavors within their experimental condition. This results in 4 cells: two flavors high-sugar beverages (n=115; 58/57 for each flavor of SSB) and the same two flavors of unsweetened control beverages (n=115; 58/57 for each flavor of control). The two-tiered randomization process allows for a fully powered test of the effects of SSB consumption (n=115) versus unsweetened control (n=115; Aim 1) and individual difference factors (Aims 2-4). Participants will complete the pre-intervention assessments (see **Table 1 & Study Procedures**), then begin the intervention which will include the daily consumption of their flavored beverage for 21 days. Following the intervention, participants will come back in the lab to complete the post-intervention assessments (see **Study Procedures**).

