## **Statistical Analysis Cover Page**

**Official Title: Neurobehavioral Plasticity to Regular Sugar-Sweetened Beverage Intake: An fMRI Experiment**

**NCT Number: NCT03490734**

**Document Date: January 25, 2023**

## **Statistical Analysis Plan**

### **A. Sample Size and Power**

Data collection was ended early due to COVID-19 (ending March 2020), resulting in a lower than anticipated sample size (160 vs. 230), which may impact results, specifically, measures of individual differences. As our sample was smaller than anticipated we performed a sensitivity analysis using Gpower (ver. 3.1.9.7, Heinrich Heine University Düsseldorf) for the primary hypothesis using alpha = 0.05, power of 0.80 and a total sample of 123 (accounting for missing data, incomplete data collection, etc.), and we are still able to detect effect of 0.25. Inclusion Criteria: Potential participants were eligible for the study if they had BMI scores between 18 and 34 at baseline. Exclusion Criteria: Individuals with probable current Axis I psychopathology or any fMRI contra-indicators (e.g., metal implants, braces) were excluded. Those with a probable Axis I diagnosis will be provided with treatment referral information and encouraged to seek treatment, current regular use (3 or more times a week) of psychoactive drugs (e.g., cocaine, marijuana, nicotine), regular smoking, serious medical problems (e.g., cancer, diabetes), dietary practices that do not allow for intake of intervention beverages.

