### **B. Analysis Plan**

#### *1. Primary and Secondary Outcomes*

Behavioral data analysis (stop-signal reaction time & perceptual ratings of beverages): Continuous variables from the stop signal task and the visual analogue scale (VAS) ratings were summarized by descriptive statistics (e.g., mean, SD, range, median), examined via graphical analyses (e.g. histogram, Q-Q plot) and analyzed to assess the normality of the data. Data transformation of continuous variables were used as necessary. Model assumptions and potential outliers were analyzed with various modeling diagnostics and plotting techniques. Two analytic datasets are used. Participants that provided data at baseline and follow-up are used in a completers analysis (CA). An intent-to-treat (ITT) dataset, including all participants that were consented and completed one assessment, are also used. In that analysis, missing data are addressed via multiple imputation methods. Of note, in both the CA and ITT all subjects are included independent of their adherence to the intervention.

For **Aim 3**, reaction times from the stop signal task (SST) are analyzed. Following previous standards, reaction times <50 milliseconds are excluded (occurred prior to imputation). As we are not analyzing inhibition (inhibition accuracy/SSRT), no other exclusion criteria were used. Data from pre- and post-intervention SST measures are analyzed using PROC MIXED implemented in SAS (Version 9.4, Cary, NC). All available data from those completing the pre- and post-intervention behavioral visits (separate from the scan assessments) are used in the completers analysis. All those who consented are included in the ITT analysis with missing data imputed. Outcome variables assessed via the SST task are: mean reaction time, standard deviation, go accuracy of the assigned beverage (pre-/post-intervention). Each of the outcome variables is entered into 2x2 repeated measure mixed models, including group-by-time interactions. Control variables of no interest to be included are BMI, assigned flavor, and gender. Interactions are probed for pairwise comparisons using least-squared mean comparisons, specifically of a priori contrasts of interest: between-group baseline differences and follow-up differences, and within-assignment change from pre- to post-intervention. Bonferroni-adjusted two-tailed *p*-values less than 0.05 are considered significant.

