## 2. *Exploratory Outcomes*

Behavioral data analysis (questionnaire scores): Questionnaires administered during the study assessments (FFQ, BIS-15, FCI, DEBQ, IPAQ, Handedness, SPSRQ, YFAS, BIS/BAS, PFS) were scored per each questionnaire's instructions and different subscales were created for each questionnaire (e.g. DEBQ restrained eating subscale). Subscale scores were examined via graphical analyses (e.g. histogram, Q-Q plot) and analyzed to assess the normality of the data. Data transformation of continuous variables were used as necessary. Model assumptions and potential outliers were analyzed with various modeling diagnostics and plotting techniques. Data from pre- and post-intervention subscale scores are analyzed using PROC MIXED implemented in SAS (Version 9.4, Cary, NC). All available data from those completing the pre- and post-intervention behavioral assessments (separate from the scan assessments) are used in the analysis. Outcome variables assessed via the different questionnaires and included in the analysis are: DEBQ restrained eating, FFQ average daily total kcal consumed, FFQ percent of daily kcal from fat, FFQ percent for daily kcal from sugar, BIS-15 total impulsivity, FCI total food craving score, SPSRQ sensitivity to punishment, SPSRQ sensitivity to reward, BIS/BAS behavioral approach score, BIS/BAS behavioral inhibition score, PFS total score, YFAS total score, IPAQ total physical activity MET. Each of the outcome variables is entered into 2x2 repeated measure mixed models, including group-by-time interactions. Control variables of no interest to be included are BMI, assigned flavor, and gender. Interactions are probed for pairwise comparisons using least-squared mean comparisons, specifically of a priori contrasts of interest: between-group baseline differences and follow-up differences, and within-assignment change from pre- to post-intervention. Bonferroni-adjusted two-tailed  $p$ -values less than 0.05 are considered significant.

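### The nine questionnaire outcomes measured at both visits should be adjusted for their own baseline, and the between-arm baseline contrast should leave the Bonferroni family

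*SAP*

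**What the plan says.** SAP B.2 (Exploratory Outcomes) names 13 questionnaire outcomes: DEBQ restraint, three FFQ measures, BIS-15, FCI, two SPSRQ scores, two BIS/BAS scores, PFS, YFAS and IPAQ. The model is given as "Each of the outcome variables is entered into 2x2 repeated measure mixed models", with group-by-time interactions. The Aim 3 paragraph of SAP B.1 uses the same sentence for its three stop-signal outcomes: "Each of the outcome variables is entered into 2x2 repeated measure mixed models, including group-by-time interactions". In both places the covariates are set out alike: "Control variables of no interest to be included are BMI, assigned flavor, and gender". The baseline value of the outcome enters as a repeated response, not as a covariate.

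Interactions are then probed by contrasts listed as "between-group baseline differences and follow-up differences, and within-assignment change from pre- to post-intervention". Bonferroni-adjusted two-tailed p-values below 0.05 count as significant. Neither section gives the size of the Bonferroni family or says whether the interaction test belongs to it.

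The Protocol randomises participants to arm (Section C), stratified by sex and BMI (Section D). Section F.1 lists all the questionnaires before the intervention. Section F.5, the post-intervention behavioral visit, does not list SPSRQ or BIS/BAS.

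**The concern.** With two visits and complete data, the group-by-time term is the difference between arms in mean change. Subtracting the whole baseline removes too much when pre and post are imperfectly correlated, and the excess is noise. If randomisation gives both arms the same expected baseline, regressing the post value on the pre value estimates the same effect with less variance. The three planned covariates do not supply this: as time-constant main effects they cancel out of the change.

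The list of probes also includes "between-group baseline differences and follow-up differences". For a questionnaire score, a baseline difference between randomised arms is chance, so testing it answers no study question, yet it can take a share of the Bonferroni allowance. The follow-up contrast beside it ignores each participant's own baseline.

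At stake is precision, not validity, in a trial that stopped at 160 of 230 participants (SAP A).

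**Working it through.** **1. The plan's own figure.** SAP A reports a sensitivity analysis "using alpha = 0.05, power of 0.80 and a total sample of 123", and concludes "we are still able to detect effect of 0.25". A two-group F test at N = 123 reaches 80% power at f = 0.2546 (78.5% power at 0.25), a paired test at dz = 0.2546 and a correlation at r = 0.2503. So 0.25 can be reproduced, but not as a group-by-time effect: the G*Power within-between interaction would give 0.127 at ρ = 0.5 and 0.180 at ρ = 0. The figure is for the primary hypothesis and says nothing about questionnaire power. The 80% below is therefore only an illustrative starting point.

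**2. Variance.** Assume equal arms, a common SD σ and pre/post correlation ρ.

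- Difference in change: (4/N) × 2(1−ρ)σ²
- Baseline-adjusted (ANCOVA): (4/N) × (1−ρ²)σ²
- Ratio: (1−ρ²) / [2(1−ρ)] = (1+ρ)/2, whatever N is

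Simulation at N = 123 (6,000 runs per setting, equal expected baselines) gave ratios of 0.655, 0.755, 0.850 and 0.942 at ρ = 0.3, 0.5, 0.7 and 0.86. The formula gives 0.65, 0.75, 0.85 and 0.93. Neither method was biased.

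**3. Questionnaires.** The documents give no pre/post correlation. The retest values in Protocol G are the nearest stand-ins. New power is Φ(2.802/√ratio − 1.960), where 2.802 = 1.960 + 0.842.

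| Scale | Stated retest r | Ratio | Variance saved | 80% power becomes |
|---|---|---|---|---|
| PFS | 0.77 (4 months) | 0.885 | 11.5% | 84.6% |
| FCI | 0.86 (2 weeks) | 0.930 | 7% | 82.8% |
| BIS-15 | 0.88 (2 weeks) | 0.940 | 6% | 82.4% |

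IPAQ has a stated reliability of 0.80 without its type or interval. Read as a retest value, it gives (1 + 0.80)/2 = 0.90, a 10% saving. DEBQ restraint, the FFQ measures and YFAS have no usable value.

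**4. How many outcomes.** At both visits: DEBQ 1 + FFQ 3 + BIS-15 1 + FCI 1 + PFS 1 + YFAS 1 + IPAQ 1 = 9. The other four (SPSRQ 2, BIS/BAS 2) have no scheduled post value, so neither model can be fitted to them.

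**5. Multiplicity.** Counted singly, the contrasts are one baseline, one follow-up and two within-arm changes. The Aim 4 paragraph counts the same structure as four. If that is the family, 0.05/4 = 0.0125 becomes 0.05/3 = 0.0167 without the baseline test. A contrast with 80% power at 0.0167 has 77.0% at 0.0125.

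**6. Aim 3.** No ρ is given for reaction time. Over an assumed 0.3 to 0.9, plain ANCOVA would save 35% to 5%. But the baseline is measured on the assigned drink's logo, which differs by arm. Let δ be a lasting reaction-time difference between the logos, in SD units. Group-by-time cancels δ; ANCOVA is biased by (1−ρ)δ. At δ = 0.3 that is 0.21, 0.15, 0.09 and 0.04 at ρ = 0.3, 0.5, 0.7 and 0.86 (simulated: 0.213, 0.154, 0.089, 0.041).

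The variance saved is (4/N)(1−ρ)² and the squared bias is (1−ρ)²δ². ANCOVA therefore has the larger mean squared error once δ exceeds 2/√N, which is 0.18 SD at N = 123, for any ρ. (That N is borrowed; the Aim 3 number is not stated.)

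One form of adjustment avoids this bias. Each participant does three baseline runs with each logo (Protocol G, stop signal task). The mean over both logos has equal expectation in the arms by randomisation, so the change score can be adjusted for it. Assume a between-logo baseline correlation of 0.8, and that the post value correlates ρ with each. The mean then has variance (1 + 0.8)/2 = 0.9, and its covariance with the change is ρ − 0.9. The share of change variance removed is (ρ−0.9)² / [0.9 × 2(1−ρ)]: 0.16/0.90 = 17.8% at ρ = 0.5, and 0.04/0.54 = 7.4% at ρ = 0.7.

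**The case against.** The planned analysis is valid and unbiased, and for Aim 3 it tests the interaction that the Protocol hypothesises. All of that stands.

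A reader might infer that Aim 3 should move to baseline adjustment too, with nothing to lose. The documents do not support this. Protocol G describes the logos as novel and similar in complexity, which makes equal baselines plausible. It does not say they were equated for reaction time, and no counterbalancing of symbols between the sweetened and unsweetened versions is described. Protocol F.1 also lists tasting before the task. Randomisation does not guarantee equal expected baselines when the arms respond to different stimuli. Aim 4 has the same difficulty more strongly, because the drink itself differs.

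A reader might also expect a gain of about 25%, which is the figure at ρ = 0.5. Nothing in the documents supplies that correlation; their own retest values point to about 6-12%. Nor do they show that the baseline contrast weakens the interaction test: the contrasts are described as probes of it, and its place in the Bonferroni family is not stated. To call the model unadjusted would be wrong as well, since three covariates are in it.

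On timing, data collection ended in March 2020 and the SAP is dated January 2023, so a change of model could look data-driven. That calls for a dated record of the change. It is a further reason not to replace the main Aim 3 analysis.

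**Conclusion.** The point holds for the nine questionnaire outcomes scheduled at both visits. Their scores do not depend on the assigned drink, so randomisation gives equal expected baselines, and adjustment is more precise for any ρ below 1. The gain is modest: 6% to 11.5% less variance for the three scales with a stated retest value, or 80% power rising to about 82-85%. This rests on retest values standing in for the trial's pre/post correlation and on similar SDs at the two visits.

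The baseline contrast has no inferential use for these scores. Its cost, 0.0125 against 0.0167, rests on a family of four per outcome and falls on the remaining probes only.

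For Aim 3 the planned interaction should remain the main analysis. Baseline adjustment there is a sensitivity analysis with a gain that cannot be fixed from the documents. Aim 4 is not affected.

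**What to change.** - **Nine questionnaire outcomes:** in SAP B.2, keep PROC MIXED but constrain the arms to a common baseline mean (time and group-by-time, no group main effect, unstructured covariance), or regress the post value on the pre value. Keep BMI, flavor and gender.
- **Contrasts:** remove the between-arm baseline contrast from the adjusted family and show baseline values descriptively. Keep the within-arm changes. State the family size and whether the interaction belongs to it. Under a common baseline, the follow-up arm difference and the group-by-time term are the same test, so give its alpha once.
- **SPSRQ and BIS/BAS:** reconcile Protocol F.5 with SAP B.2. Either record that these were given after the intervention, or drop their four scores from the pre/post analysis.
- **Aim 3:** keep group-by-time as the main analysis. Add, labelled as sensitivity, either plain baseline adjustment or the change score adjusted for the baseline mean over both logos; the latter is robust to a lasting logo difference. A within-person comparison of the two logos at baseline would show whether one exists.
- **Aim 4:** no change.

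The cost is a few model statements and SAP sentences, with no new data. Date the amendment and, if results have already been seen, report the planned group-by-time estimates alongside.

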### D. Study Duration, Enrollment and Number of Subjects

For each participant, the study will include 2 pre-intervention visits, 2 post-intervention visits, and 9 in-lab assessments during the 21-day intervention period. Total study duration will be approximately two years. We will recruit 230, 18-28-year-old healthy individuals. Stratified randomization techniques will be used to distribute: 1) male & females, 2) those with a BMI > 26.1 & those with a BMI < 26.1 equally across the 2 experimental conditions (SSB vs. unsweetened beverage) and then to the two flavors within each experimental condition. BMI of 26.0 was selected as it is the midpoint of inclusion criteria 18 < BMI < 34. Experimental and flavor conditions will be blinded to those performing analyses.

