For **Aim 4**, perceptual hedonic, taste and internal state ratings (assessed using visual analog scales (VAS)) are analyzed. Data from pre- and post-intervention perceptual ratings are

analyzed using PROC MIXED implemented in SAS (Version 9.4, Cary, NC). Pleasantness and Desire of the assigned beverage (pre-/post-intervention) are each entered into 2x2 repeated measure mixed models, including group-by-time interactions. Control variables of no interest to be included are BMI, assigned flavor, gender, and thirst. Four pairwise comparisons of interest (pre- and post-intervention differences by intervention assignment and within-assignment change over time) are probed. Tukey-adjusted two-tailed  $p$ -values less than 0.05 are considered significant.

**fMRI data preprocessing:** Neuroimaging data were preprocessed using the fMRIPrep pipeline. DICOMS were converted to the Brain Imaging Data Structure (BIDS file structure), then preprocessed using fMRIPrep. Prior to preprocessing, the first four volumes of each functional run were trimmed. fMRIPrep preprocessing included skull stripping using Advanced Normalization Tools (ANTs); tissue segmentation using FSL's Automated Segmentation Tool (FAST); and spatial normalization to Montreal Neurological Institute (MNI) 152-Asymmetrical space using ANTs' registration option. Functional data were co-registered to anatomical data using FSL's FMRIB's Linear Image Registration Tool (FLIRT) with boundary-based registration. Functional data were additionally motion corrected using FSL's MCFLIRT and corrected for fieldmap distortion. In FSL, final preprocessing included spatial smoothing using a 5mm full width half maximum isotropic Gaussian kernel, high-pass filtering, adding temporal derivatives, adjusting for autocorrelation, and adjusting for nuisance regressors, including the 6 motion parameters, 6 anatomical component-based noise correction regressors (aCompCor), and high motion time points (FD>0.5mm). A functional run for a subject was excluded if >30% of total volumes were flagged as high motion points.

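### In the Aim 3 and exploratory models, BMI, flavor and gender as main effects cancel from the group-by-time test, so the stated control does not act on the tested effect

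*SAP*

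**What the plan says.** - **Aim 3** (SAP B.1). Mean reaction time, its standard deviation and go accuracy each go into a 2x2 repeated-measures model in PROC MIXED. The only interaction named is group by time. "Control variables of no interest to be included are BMI, assigned flavor, and gender". The planned contrasts are between arms at baseline, between arms at follow-up, and pre to post within each arm.
- **Exploratory questionnaires** (SAP B.2). Same model form and same three covariates.
- **Aim 4** (SAP B.1). Same form with one addition: "Control variables of no interest to be included are BMI, assigned flavor, gender, and thirst".
- **Hypothesis** (Protocol B, Aim 3). The effect of interest is the interaction of assignment and time on mean Go reaction time.
- **Datasets** (SAP B.1). The completers set requires baseline and follow-up. The intent-to-treat set is filled by multiple imputation.
- **Randomization** (Protocol D): "Stratified randomization techniques will be used to distribute: 1) male & females", and likewise BMI above and below 26.1, across the two conditions. Flavor is assigned in a second step within condition (Protocol C and D).
- **fMRI Level 3** (SAP B.1). BMI, flavor and gender are among the covariates, and the data analysed are within-subject differences between visits.

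**The concern.** Someone who reads that the models control for BMI, flavor and gender will assume that the hypothesised interaction is adjusted for them. With two visits, that interaction is the between-arm difference in post-minus-pre change, and a covariate constant over the two visits cannot explain change unless it is allowed a different effect at each visit. The listed control would then act only on the single-visit contrasts.

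Two things are at stake. One is precision: sex and BMI were thought important enough to stratify on, and the trial stopped at 160 of 230 participants, so any cheap gain is worth having. The other is description: the same three covariates adjust the tested change in the fMRI models but not in Aim 3.

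**Working it through.** **Inputs.** From SAP A: "using alpha = 0.05, power of 0.80 and a total sample of 123", and the statement that "we are still able to detect effect of 0.25" (metric not named). Tests are two-sided ("Bonferroni-adjusted two-tailed", SAP B.1). Allocation is 1:1 by design ("n=115; 58/57 for each flavor of SSB", with the same numbers for control, Protocol C). The documents do not give the variance of change or the share of it that the covariates explain; the latter is assumed below.

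**The plan's own figure.** For a two-group F test with 1 and 121 degrees of freedom and noncentrality N·f² = 123 × 0.25² = 7.69, power is 0.785. The smallest f with power 0.80 is 0.2546. The stated 0.25 is therefore reproduced as a two-group comparison without covariates. As a standardised difference in change this is 2 × 0.2546 = 0.509.

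**Algebra.** Let G be arm, t = 0 or 1 the visit, and X the three factors:

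Y = a + bG + ct + dGt + γ'X + error.

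The within-person change is D = c + dG + (difference of errors). The term γ'X is gone. Written as two equations, baseline has regressors (1, G, X) and change has (1, G). When one equation's regressors are a subset of the other's, generalised least squares for the smaller equation reduces to ordinary least squares. So d, and the within-arm changes c and c + d, do not depend on X under a random-intercept or an unstructured covariance. The single-visit contrasts b and b + d do depend on X.

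**Numerical check.** Three simulated complete datasets; the first has N = 123 with 62 and 61 per arm, the other two N = 123. Entries are the group-by-time estimate (SE).

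| Dataset | No covariates | Main effects | Covariate-by-time added | SE ratio |
|---|---|---|---|---|
| 1 | -0.185 (7.796) | -0.185 (7.796) | -3.611 (7.564) | 0.970 |
| 2 | -7.652 (7.889) | -7.652 (7.889) | -8.489 (7.532) | 0.955 |
| 3 | -18.963 (8.843) | -18.963 (8.843) | -19.445 (8.96) | 1.013 |

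Datasets 1 and 2 were built so that sex and BMI predict change. They show the mechanism, not the size to expect in this trial. In dataset 1 the covariate-by-time result equals the regression of change on arm and the three covariates. In the same dataset the main effects do move the between-arm difference at follow-up, from -8.85 to -13.32 (unstructured covariance).

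**Aim 4.** Thirst is rated at both behavioral visits (Protocol F), so it can vary within a person and does not cancel. Its coefficient draws partly on between-person information, so the fixed factors also enter slightly. In four simulated datasets in which thirst affects the rating:

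| | 1 | 2 | 3 | 4 |
|---|---|---|---|---|
| No covariates | -0.616 | -5.217 | 1.973 | 3.592 |
| Thirst only | 0.294 | -4.047 | 0.330 | 3.373 |
| Thirst and three factors | 0.220 | -4.138 | 0.420 | 3.384 |
| SE of last row | 3.582 | 4.285 | 3.965 | 3.291 |

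The three factors move the estimate by at most 0.091, about 0.02 of its SE.

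**Size of the possible gain.** If the factors explain a share R² of the sample variance of change and are balanced between arms, the SE ratio is √[(1 − R²) × 121/118], since the residual degrees of freedom fall from 121 to 118.

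| Assumed R² | SE ratio | Detectable difference (0.509 × ratio) |
|---|---|---|
| 0 | 1.013 | 0.515 |
| 0.02 | 1.002 | 0.510 |
| 0.05 | 0.987 | 0.502 |
| 0.10 | 0.961 | 0.489 |

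Break-even is at R² = 3/121 = 0.025. Chance imbalance reduces the gain: in dataset 1, with R² = 0.110, the formula gives 0.955 but the fitted ratio was 0.970.

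**The case against.** The strongest reply is that the plan is valid as it stands. Randomization was stratified on sex and BMI, so the unadjusted interaction is not biased; the covariates do work on the planned single-visit contrasts; and the gain is small and rests on an assumed R². All of that stands. A reader might infer bias, or that the covariates do nothing, and neither follows.

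Further limits also stand:

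- The SAP prints no MODEL statement. Main effects only is the plain reading, not an explicit one.
- The SAP does not say which BMI value is used, and weight is measured at each assessment (Protocol G). A visit-specific BMI would not cancel exactly (0.076 against -0.185 in dataset 1), but it would adjust for weight change after randomization, not for the stratum.
- In the intent-to-treat set the factors could still act through the imputation model, which is not described. The cancellation holds within each imputed dataset.
- It is tempting to say that Aim 4 is exactly unadjusted too. Thirst rules that out.
- It is tempting to call all three factors stratifiers. Flavor is a second-step randomized assignment.
- Level 3 takes within-subject change as its input, so its covariates act on change by construction. The contrast with Aim 3 need not be a deliberate choice, but the listed control still means different things in the two places.

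None of this makes baseline main effects act on the Aim 3 interaction in completers.

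**Conclusion.** The point holds for the Aim 3 and exploratory models, given main-effect covariates, baseline BMI and both visits present: the group-by-time test and the within-arm changes are unadjusted for BMI, gender and flavor. In Aim 4 the interaction is adjusted for thirst but hardly at all for the three fixed factors.

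The consequence is modest. At an assumed R² of 2-10% the SE would fall by about 0-4% at N = 123. At the top of that range the gain is worth roughly 123 × (1/0.961² − 1), or about 10 participants. A reader might expect a 1-5% gain from √(1 − R²) alone, but that leaves out the cost of three parameters. If the factors do not predict change, the SE rises by about 1%. The documents give no basis for choosing within this range. This is a worthwhile low-cost correction, not a threat to validity.

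**What to change.** In the Aim 3, Aim 4 and exploratory models, state that BMI is the baseline value and add BMI-by-time, gender-by-time and flavor-by-time terms. For Aim 3 and the exploratory outcomes, regressing post-minus-pre change on arm and the three covariates is equivalent. Level 3 of the fMRI analysis already treats change this way.

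The cost is three terms in the PROC MIXED statement, one or two SAP sentences, and three of 121 degrees of freedom. Because the SAP is dated after data collection ended, the change should be recorded as an amendment and the interaction also shown without the added terms.

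If the models are kept as they are, the report should say that the covariates adjust only the single-visit between-arm contrasts, and should not describe the interaction test as controlled for BMI, gender and flavor.
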